9.4 Procedures for Handling Withdrawals

The Investigator (or delegate) must complete the reason for withdrawal and the date of withdrawal of a participant in the appropriate section of the participant's CRF. If more than one reason applies, then the main reason for withdrawal should be indicated.

In the event that a participant becomes pregnant at any time during the study period every attempt will be made to follow her to term (although study participant has the option to decline further follow-up), the outcome of the mother and infant documented as per Section 8.9.

9.5 Replacement of Withdrawn Participant

Any participants who discontinue the clinical study of their own volition or who are discontinued by the investigator may be replaced at the discretion of Starpharma, irrespective of whether they have been assigned a PIN and have received a dose. Replacement of withdrawn participants will only be performed if an on-study withdrawal rate of more than 15% is observed during the study and following 50% of planned recruitment.

9.6 Lost to Follow-Up

At the start of the study each study participant will state how they can be contacted during the study. These contact details will be recorded in the participant's address file. If a participant fails to appear for a scheduled visit, at least three attempts to contact them should be made over the subsequent 7 days. These attempts should be documented in the participant's study file. After these three attempts, no further efforts need be made to find them, but their file should remain open until study closeout.

If the participant does not return to the clinic before the study is closed, the CRF should be checked to indicate that the participant was lost to follow-up. The "loss to follow-up" designation cannot be made for any participant until the closing date of the study.

9.7 Premature Termination of Study

The study may be terminated prematurely by the Investigator or his/her designee, the Sponsor, government or regulatory authorities, or site IRB/IECs if:

- The number and/or severity of AEs justify discontinuation of the study;
- New data become available that raises concern about the safety of the investigational product, so that continuation might cause unacceptable risks to subjects.

In addition, Starpharma reserve the right to discontinue the trial prior to inclusion of the intended number of subjects, but intend only to exercise this right for valid scientific or administrative reasons.

After such a decision, the Investigator must contact all participating subjects within two weeks, and written notification must be sent to the Ethics Committee.

9.8 Notification of Primary Care Physician

If the study participant consents, her primary care physician will be notified of her inclusion in the study. If desired, the participant may be given an open letter for her to hand to her primary care physician during the follow-up stage of the study so that AEs may be reported.

10. STATISTICAL CONSIDERATIONS

10.1 Review of Study Design

The primary aim of this randomized, double-blind, dose-ranging study is to determine the efficacy and safety of three different strengths of SPL7013 Gel (0.5%, 1% and 3%) compared with HEC placebo gel, when administered each night for seven consecutive days in women with a diagnosis of BV. Efficacy will be determined in a number of different ways; as Clinical Cure, Nugent Cure, and Therapeutic Cure at the Test of Cure Visit (Day 21-30). Initial efficacy will be determined immediately post completion of the course of treatment by assessment of these parameters at Visit 2, on Day 9-12 and also at Baseline. Safety will be determined via assessment of signs and symptoms of genital irritation and other AEs.

10.2 Criteria for Evaluation of Study Objectives

10.2.1 Primary Endpoints

The endpoint for evaluation of primary study objective (Primary Endpoint) is as follows:

• "Clinical Cure" at the Test of Cure (TOC) visit as defined by no abnormal discharge, as described by the Amsel's criterion for vaginal discharge, and fulfilling no more than one of the other three criteria.

10.2.2 Secondary Endpoints

The endpoints for evaluation of secondary study objectives (Secondary Endpoints) are as follows:

- "Nugent Cure", "Therapeutic Resolution of BV" and "Therapeutic Cure" at the TOC visit
- "Clinical Cure", "Nugent Cure", "Therapeutic Resolution of BV" and "Therapeutic Cure" at Day 9-12 (Visit 3)
- Both Investigator-assessed and patient perceived resolution of symptoms compared to Baseline, as determined in the "Symptom Questionnaire"
- Genital AEs considered to be possibly, probably, definitely related to study product
- All other AEs
- Acceptability of study treatment as determined in the "Acceptability Questionnaire" (the TSOM).
- To assess the correlation of BV signs and symptoms (via Symptom Questionnaire) with clinical diagnosis of BV
- Semi-quantitative analysis of vaginal flora (sub-set only)

10.2.3 Definition of Signs and Symptoms of Genital Irritation

The following cluster of symptoms will be employed in determining the number of women with signs and symptoms of genital irritation, and will be actively solicited in the CRF and diary card:

Symptoms:

Pelvic pain; vaginal and vulvar pain; tenderness; vulval itching, edema, erythema, lesions (vesicles, blisters, erosions, ulcers), or rash; vaginal itching, dryness, excessive discharge; dysuria; vulvovaginitis; or dyspareunia.

Signs:

Vulval edema, erythema, lesions (vesicles, blisters, erosions, ulcers), or rash; vaginal edema, erythema, excessive discharge or lesions; cervical edema, erythema, discharge, or lesions; vulvovaginitis; or cervicitis.

Each AE considered to be a symptom or sign of genital irritation will be identified as such in the CRF, and additionally will be noted as either being reported by participant (either spontaneously or in the diary card) or detected at pelvic/genital exam.

10.2.4 Definition of Clinical, Nugent, Therapeutic Cure

10.2.4.1 Clinical Cure

Clinical Cure is defined as the resolution of BV according to Amsel's criteria (*i.e.* no abnormal discharge, as described by the Amsel's criterion for vaginal discharge, and fulfilling no more than one of the other three criteria, when all four were present at Baseline: presence of white to grey homogeneous discharge; positive whiff test (amine odor) with addition of potassium hydroxide (KOH); vaginal pH greater than 4.5; and presence of clue cells).

10.2.4.2 Nugent Cure

Nugent Cure is defined as the absence of BV and normalization of vaginal microflora according to the Nugent scoring criteria (*i.e.* a Nugent score of 3 or less when a score of 7 or more was determined at Baseline).

10.2.4.3 Therapeutic Cure

Therapeutic Cure is a composite endpoint defined as the absence of BV according to both the Amsel's and Nugent scoring criteria (*i.e.* no abnormal discharge fulfilling the description of the Amsel's criteria and presence of either one or none of the remaining three symptoms identified in the criteria and a Nugent score of 3 or less irrespective of status at Baseline).

10.2.4.4 Therapeutic Resolution of BV

Therapeutic Resolution of BV is a composite endpoint defined as "Clinical Cure" and a shift to intermediate or normal flora according to the Nugent scoring criteria (i.e. no abnormal vaginal

discharge fulfilling the description of the Amsel's criteria and presence of either one or none of the remaining three symptoms identified in the criteria and a Nugent score of 6 or less irrespective of status at Baseline).

10.2.5 Definition of "Treatment Non-Responders"

Women who report no improvement in the abnormal vaginal discharge associated with BV by Visit 3 (Day 9-12) and receive rescue therapy prior to the TOC Visit (Day 21-30) are considered to be "Treatment Non-Responders".

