6.8 Rescue Medication

As it may take a couple of weeks for BV to fully resolve and the vaginal environment to return to normal, every effort should be made to retain study participants in the trial up to the final visit (Visit 4, TOC). However if participants are not satisfied that symptoms are improving, rescue medication/therapy may be provided if:

- at Visit 3, the study participant reports no improvement in BV-associated discharge and wishes to receive alternative therapy;
- after Visit 3 but prior to Visit 4, the study participant reports that symptoms have returned and wishes to receive alternative therapy.
- at Visit 4 the investigator determines that the BV has recurred, or study participant reports that symptoms have returned.

Prior to administration of rescue therapy, participants are to be assessed as per their next scheduled study visit (*i.e.* Visit 3 or Visit 4 (TOC)). Rescue medication will be the standard therapy for BV according to local practice at the study site. Details of any rescue medication provided to a study participant must be entered in to the CRF, and marked as such. Study participants who receive rescue therapy prior to Visit 4 (TOC) are considered to be "Treatment Non-Responders". Women who receive rescue therapy will continue to be assessed during the remaining study visits.

Medication may also be provided by the study participant's primary care physician after the participant has completed the study if her BV recurs after Visit 4. No details of any therapy received after completion of the study is to be provided.

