6.9 Other Concomitant Medication/Treatment

Apart from rescue medication as outlined above, there are no concomitant medications that are to be specifically used as part of this study.

Vaginally administered products (lubricants, menstrual hygiene products (except tampons), contraception products, etc.) and oral antifungals are discouraged but should not lead to withdrawal if commenced during the study; however, the use of these is the basis for exclusion

criteria at Screening/Baseline. Antibiotics by any route are excluded during the on-study period unless provided for rescue therapy as per Section 6.8 as they will confound the study endpoints. Vaginally administered anti-fungals are also excluded during the on-study period. Women who receive antibiotic treatment (via any route) or vaginal antifungals during the study will cease study medication, but continue to be assessed during the remaining study visits. These women will not be included in the determination of the efficacy endpoints. Refer to Section 7.3.5 for more detail. Apart from concomitant medications specifically excluded under the inclusion/exclusion criteria, there are no other restrictions on concomitant treatments.

All concomitant medications administered from Screening to Follow-up must be recorded in the CRF.

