7.1.3 Visit 3 (Day 9-12)

Visit 3 will be scheduled for Day 9-12, after completion of treatment. This visit should be scheduled prior to the anticipated date of onset of menses. If menses is due to occur or actually occurs on Day 9 then the visit may be delayed until complete cessation of bleeding.

This visit will include the following procedures:

- Review of protocol compliance
- · Review diary card
- Review of AEs and concomitant medications (see Sections 7.3.5 and 8)
- Completion of Symptom Questionnaire (see Section 7.2.7)
- Completion of Acceptability Questionnaire [TSQM] (see Section 7.2.8)
- Pelvic examination including vaginal swab for Gram stain, semi-quantitative analysis (subset only) and storage sample (see Sections 7.2.3 and 7.2.6)
- Assessment of BV according to the Amsel's Criteria
- Issue diary card for follow-up period and provide instructions for completion
- Collect used and unused applicators

Women who report no improvement in vaginal discharge associated with BV who wish to receive further treatment will be offered rescue therapy according to Section 6.8. These study participants will be considered "Treatment Non-Responders", and will not attend the TOC visit. Instead, these participants will receive a telephone call at the time that the TOC would be scheduled to assess response to rescue medication and any adverse effects (*e.g.* candidiasis). Participants will be referred to their primary care physician for any ongoing AEs as appropriate. Any ongoing SAEs should be followed until resolution.

Each participant is then provided with the date of the last scheduled visit, the Follow-Up visit.

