7.1.4 Visit 4 (Day 21-30) – Test of Cure (TOC)

Visit 4 (TOC) will be scheduled for Day 21-30, and will include the following procedures:

- Review of protocol compliance
- Review diary card
- Review of AEs and concomitant medications (see Sections 7.3.5 and 8). Participant will be referred to her primary care physician for any ongoing AEs as appropriate. Any ongoing SAEs should be followed until resolution or considered as stable.
- Completion of Symptom Questionnaire
- Pelvic examination including vaginal swab for Gram stain, semi-quantitative analysis (subset only), and storage sample (see Sections 7.2.3 and 7.2.6)
- Assessment of BV according to the Amsel's Criteria. Women who suffer a recurrence of BV symptoms who wish to receive further treatment will be provided with treatment for her BV according to local practice (see Section 6.8). Any rescue therapy will be documented in the participant's CRF.
- Pregnancy testing (see Section 7.2.6)

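### The rescue rules conflict between Section 6.8 and Sections 7.1.3, 9.2 and 10.2.5, and none scores rescue before Test of Cure as failure, so a reading after rescue antibiotics can count as a cure

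*Protocol*

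**What the plan says.** **Who is a Treatment Non-Responder.** Section 6.8 is broad: "Study participants who receive rescue therapy prior to Visit 4 (TOC) are considered to be" Treatment Non-Responders. It expressly allows rescue for relapse, where "after Visit 3 but prior to Visit 4, the study participant reports that symptoms have returned and wishes to receive alternative therapy". The statistical definition in 10.2.5 is narrow, with TOC as the time limit on which the quoted clause ends: "Women who report no improvement in the abnormal vaginal discharge associated with BV by Visit 3 (Day 9-12) and receive rescue therapy prior to". Sections 7.1.3 and 9.2 likewise tie the label to no improvement at Visit 3.

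**Who attends TOC.** Section 6.8: "Women who receive rescue therapy will continue to be assessed during the remaining study visits". Section 7.1.3: "Women who report no improvement in vaginal discharge associated with BV who wish to receive further treatment will be offered rescue therapy"; these women are Non-Responders "and will not attend the TOC visit" and are telephoned instead. Section 9.2 says only that they are not required to attend.

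**How rescue enters the analysis.** Section 6.9 says antibiotics are "excluded during the on-study period unless provided for rescue therapy as per Section 6.8 as they will confound the study endpoints". The MITT dataset (10.2.6.3) excludes women given antibiotics but exempts those who had them as rescue. Clinical Cure (10.2.4.1) is defined by Amsel findings alone. Section 10.8 fills missing and out-of-window values by LOCF where appropriate. Section 10.9 runs the primary analysis on MITT (LOCF), MITT (as observed) and per-protocol data.

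**When TOC is.** Section 7.1.4: "Visit 4 (TOC) will be scheduled for Day 21-30".

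**The concern.** Rescue is standard BV therapy. A woman who needs it before TOC was not cured by the study gel, or did not stay cured, and a later normal examination reflects the rescue drug. The protocol recognises that antibiotics confound the endpoints, yet it keeps rescued women in the efficacy dataset and gives no scoring rule for them. The Non-Responder label suggests that failure was intended, but no endpoint or dataset definition uses it.

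The conflict over attendance makes this practical. Whether a rescued woman has a post-rescue TOC reading depends on which section her site follows. At stake is the primary endpoint in a trial with 28 evaluable women per arm, where a few scoring decisions can change whether the overall test is passed.

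**Working it through.** **1. Follow one woman through the text.** She reports no improvement at Visit 3, is rescued that day, and her Amsel findings are normal at Day 21-30.

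| Rule followed | TOC reading | MITT (LOCF) | MITT (as observed) |
|---|---|---|---|
| 6.8: stays under assessment | Yes, after antibiotics | Cured | Cured |
| 7.1.3: telephone call only | None | Visit 3 value, usually not cured | No value |

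Under 6.8 her reading is observed and in window, so neither LOCF nor the as-observed analysis removes it. She also stays in the per-protocol analysis unless blinded review takes her out, because the listed criterion concerns excluded medication and 6.9 does not exclude rescue.

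**2. Follow a relapser.** She is cured at Visit 3, relapses, and is rescued before Day 21. Section 6.8 requires her to be assessed beforehand as for her next scheduled visit, which is Visit 4. Her Visit 3 cure stands at TOC only if the analysis window in the SAP excludes that early assessment and LOCF reaches back past it. If the early assessment is itself carried forward, she is not cured. Section 10.8 leaves the windows undefined, so either outcome fits the text.

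**3. Reproduce the plan's sample size.** Inputs from 10.4: 50% v 15%, two-sided alpha 0.048, power 80%, 15% drop-out. With pooled variance and p̄ = 0.325:

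n = [1.977·√(2·0.325·0.675) + 0.842·√(0.25 + 0.1275)]² / 0.35² = 27.2, so 28 per arm.

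28/0.85 = 32.9, so 33 per arm; 33 × 4 = 132. The stated figures reproduce.

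**4. Weight of one woman.** 1/33 = 3.0 points; 1/28 = 3.6 points.

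**5. Effect on the overall test that 10.9 requires first.** Planned counts: 0.15 × 28 = 4.2, taken as 4, on placebo; 0.50 × 28 = 14 in each active arm. Assumption: centre is ignored (one stratum), so the CMH general-association statistic is Pearson X² × 111/112 on 3 df, with X² = Σ(xᵢ − 28p̄)² / [28p̄(1 − p̄)].

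| Cures: placebo/0.5%/1%/3% | X² | × 111/112 | p |
|---|---|---|---|
| 4/14/14/14 | 11.067 | 10.968 | 0.012 |
| 5/14/14/14 | 8.909 | 8.829 | 0.032 |
| 6/14/14/14 | 7.000 | 6.938 | 0.074 |

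Against 0.048, one false placebo cure does not change the result and two do. A single woman matters only near the boundary. In a table chosen to show this, 4/6/8/12 gives p=0.097, one more cure at 3% gives p=0.0478, and one more on placebo as well gives p=0.086.

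**The case against.** The strongest reply is that endpoint scoring usually belongs in the SAP. Section 10.8 calls itself a summary, applies LOCF only where appropriate, and leaves the windows to be defined. That has force for the relapser, whose false cure depends on rules not shown. It has less force for the woman rescued at Visit 3: the endpoint, the MITT exemption and the conflicting attendance instructions are all fixed in the protocol, and an SAP cannot settle what sites do at TOC.

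Other parts of the reply stand:

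- If a relapser's pre-rescue assessment is her Visit 4, she has no visit left, so a post-rescue TOC reading arises mainly for women rescued at Visit 3. Section 9.1 also places rescue for relapse after the final visit.
- The per-protocol criteria in 10.2.6.5 are expressly non-exhaustive and may be amended before unblinding, and 10.3 provides for blinded review of evaluability. Rescued women can be removed there.
- Section 10.10 tabulates rescue for relapse across treatment groups. This shows its use but does not alter cure scoring.

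A reader might go further in four ways that the documents do not support:

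- That LOCF certainly carries a relapser's Visit 3 cure to TOC. This needs both conditions in step 2.
- That a fixed run of days between Visit 3 and Day 21 is out of window. The visit tolerance in Section 7 is not legible in the available text, and 7.1.3 lets Visit 3 be delayed for menses.
- That 7.1.6 is a third definition of Non-Responder. Its sentence only separates rescue from withdrawal.
- That power falls by a known amount. If 20% of uncured women in every arm were rescued and 70% of those then read as cured, the rates would be 0.50 + 0.50 × 0.14 = 57% and 0.15 + 0.85 × 0.14 = 27%, and pairwise power would fall from 81% to 63%. Both shares are invented, and equal use across arms is a further assumption.

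**Conclusion.** The point holds in this form. The sections conflict on who is a Non-Responder and on whether rescued women attend TOC, and no stated rule scores rescue as failure. The label mismatch alone changes no result, because no endpoint uses the label. The main consequence is that a post-antibiotic reading can count as a cure in both MITT analyses, and in per-protocol unless blinded review intervenes. The carried-forward Visit 3 cure is secondary and conditional on the SAP.

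Size and direction are unknown. The protocol gives no rescue rates and says only that relapse after therapy is common (2.1). Post-rescue cures favour arms with more rescue, and carried-forward cures favour arms with more Visit 3 cures, so the net effect could go either way. The p-values in step 5 rest on 28 per arm, exact planned counts and a single stratum; they show sensitivity and do not predict a result. The change should be made, because the primary endpoint is affected and the correction is cheap.

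**What to change.** - **10.2.5:** define a Treatment Non-Responder as any woman given BV rescue before an in-window TOC assessment, whether for no improvement or for relapse.
- **10.2.5 and 10.9:** state that she counts as not cured at TOC for all cure endpoints, whatever her LOCF or post-rescue values. Rescue given at Visit 4 after an in-window assessment leaves that assessment as the result.
- **6.8, 7.1.3 and 9.2:** adopt one attendance rule: telephone call only for women rescued at Visit 3, and a Visit 4 assessment before rescue for relapsers. Use any post-rescue reading for safety and description only.

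The cost is wording in five sections. Section 6.8 already requires rescue details in the CRF, so recording the reason for rescue adds at most one field. No extra patients or visits are needed.

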10.2.6 Description of Groups for Analysis

Analysis maybe performed on selected subgroups and presented for the primary and secondary efficacy endpoints where appropriate. Full details of any subgroups will be provided in the statistical analysis plan.

10.2.6.1 Description of Participant Completion

A participant is considered to have completed the study if they have administered at least 6 doses of study medication and attended all study visits.

10.2.6.2 Randomized Dataset

The randomized dataset will include all participants that meet the eligibility criteria and are randomized to double-blind investigational product. In determining eligibility, and in case of discrepancies, the Nugent score obtained at screening will take precedence over the score determined centrally.

10.2.6.3 Modified Intent to Treat Safety Dataset

The Modified Intent-to-treat (MITT) dataset will include all participants who are randomized to double-blind investigational product, administer at least one dose of study gel, and have at least one post baseline assessment of efficacy and did not receive antibiotics except as rescue medication (via any route) or vaginal antifungals. This dataset will be employed to determine all primary and secondary efficacy endpoints. Participants will be analyzed according to the treatment group in which they were randomized, irrespective of actual treatment received.

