7.2.6.4 Assessment of Candidiasis

The wet mount vaginal smear obtained during each pelvic exam will also be assessed for the presence of *Candida* spores. If *Candida* spores are present with symptoms of candidiasis, then oral treatment may be administered with no requirement for withdrawal post-Baseline. Once a participant has been randomized, vaginal treatments may not be administered for the period between baseline (Visit 2) and the TOC visit (Visit 4) as these may compromise the study endpoints. If oral treatment cannot be administered for the candidiasis and treatment is required prior to the TOC visit (Visit 4), then the patient must be withdrawn from the study. However, if treatment is required prior to randomization to study product, study participants will need to first be treated before randomization, and will need to comply with the inclusion/exclusion criteria (*i.e.* cannot be randomized less than 14 days after last dose of medication).

All details of candidiasis and associated treatment are to be recorded in AE and Concomitant Medication sections of the CRF. Presence of *Candida* spores alone with no symptoms of candidiasis are not to be reported as an AE.

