8.5 Toxicity Management

AEs and laboratory abnormalities will be graded as outlined in Section 8.3.

For the purpose of monitoring toxicities, Baseline is defined as the status or last value prior to the first use of study product. All management is based on changes from this initial status or value.

All grade 2 or higher laboratory abnormalities should be confirmed by repeat testing as soon as possible, preferably within 3 calendar days of receipt of results prior to dose interruption or discontinuation, unless such a delay is not consistent with good medical practice.

Study participants will be asked to contact the study site staff if they miss a dose of study medication due to an AE. Site staff will assess whether the participant should come in for an assessment, and if so, an ad hoc visit will be scheduled as soon as possible. In response to AEs reported by participants and/or observed upon exam by study staff, the study site investigator or designee will recommend either continuation or holding study product use consistent with the criteria in Section 16.3. Study product use also will be held or discontinued in the event of an SAE that is judged by the site Investigator or designee to have a potential causal relationship with study product.

Unless the participant withdraws consent, they will remain in the study to complete the safety evaluations (unless clinically contraindicated according to Table 1 and Section 16.3).

Participants requiring treatment for an STI will be withdrawn from the study. Participants who develop any other conditions requiring vaginal therapy (*e.g.* candidiasis) whilst on study where oral therapy cannot be used or antibiotics by any route, will cease study product, however they should continue with the remaining study visits.

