10.2.6.5 Per-Protocol (PP) Dataset

The Per-Protocol dataset is a subset of the Modified Intent-to-Treat dataset which includes all randomized participants who administered at least 6 doses of study product over 7 consecutive

days and who are considered sufficiently compliant with the protocol. All primary and secondary efficacy evaluations will be conducted in the Per-Protocol Dataset as supportive to the MITT analysis.

The definition of "sufficiently compliant" includes, but is not limited to:

- No violations of any study entry eligibility criteria;
- Received study treatment to which they were randomized and did not receive the wrong medication or incorrect dose at any time;
- ≥85% compliant to intended dose of Investigational Product;
- Did not receive any excluded concomitant medication prior to the time point evaluated;
- Treatment assignment was not unblinded to the subject, study site personnel, CRO, or Sponsor at any time during the study.

The criteria may be amended prior to unblinding of treatment assignment and analysis of data. Reasons for changes may include study conduct changes, protocol amendments, or changes in the appropriateness of the criteria, which may be assessed based on review of blinded data.

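### The primary efficacy set drops dosed women for medication or missing assessments after randomisation, with no time limit and no efficacy analysis that keeps them

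*Protocol*

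**What the plan says.** Protocol section 10.2.6.3 defines the MITT set. Besides randomisation and at least one dose, it sets two conditions, on assessment and on medication: a woman must "have at least one post baseline assessment of efficacy and did not receive antibiotics except as rescue medication (via any route) or vaginal antifungals". Of this set the section says: "This dataset will be employed to determine all primary and secondary efficacy endpoints".

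Section 6.9 covers women given antibiotics by any route or vaginal antifungals during the study. They stop study medication but go on being assessed at their remaining visits. It then adds: "These women will not be included in the determination of the efficacy endpoints".

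The per-protocol (PP) set in section 10.2.6.5 is a subset of the MITT. Its medication criterion is tied to the visit: "Did not receive any excluded concomitant medication prior to the time point evaluated".

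Section 10.9 analyses the primary endpoint in the MITT as observed, the MITT with last observation carried forward (LOCF), and the PP set, and treats categorical secondary endpoints in the same way. Section 10.2.6.2 defines a Randomized Dataset, but no efficacy analysis is assigned to it.

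On follow-up after a vaginal antifungal the sections disagree. Section 7.2.6.4 says that if oral treatment cannot be given and treatment is needed before TOC, "then the patient must be withdrawn from the study", and section 7.3.5 agrees. Section 8.5 says that such women "will cease study product, however they should continue with the remaining study visits", and section 6.9 agrees with that.

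**The concern.** A comparison is protected by randomisation only if membership of the analysis set does not depend on what happens after allocation. Here it does, and the protocol itself describes routes by which treatment could affect it. Section 6.11 lists dysuria, genitourinary pruritus and curdled white discharge among commonly reported events. Section 16.3.1 foresees antibiotics after urinary symptoms. Section 7.2.6.4 foresees candidiasis that cannot be treated orally.

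Two features make it worse. First, the exception for rescue covers antibiotics only. Sections 7.1.3 and 9.2 name candidiasis as a possible adverse effect of rescue therapy. A Treatment Non-Responder who then uses a vaginal antifungal is deleted, although she is a known failure.

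Second, the rule has no time point. A woman examined at Visit 3 and first given an antibiotic on Day 20 leaves the set altogether, and her Visit 3 result goes with her. The cure outcomes at Visit 3 are secondary endpoints (sections 3.2 and 10.2.2).

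At stake is whether the cure-rate differences used to choose a gel strength describe the women who were randomised, or a subset selected by later events.

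**Working it through.** **Reproducing the plan's own figures.** Inputs from section 10.4: cure rates 50% and 15%, power 80%, alpha 0.048, drop-out 15%. Tests are two-sided (section 10.8).

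n = [z(1−α/2)·√(2·p̄·(1−p̄)) + z(power)·√(p1(1−p1) + p2(1−p2))]² / (p1−p2)², with p̄ = 0.325

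= [1.977·0.662 + 0.842·0.614]² / 0.1225 = 27.2, so 28 per arm.

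Power at 28 is 81.1%. Then 28/0.85 = 32.9, so 33 per arm, and 4 × 33 = 132. The sample size is sound; the issue is who is counted.

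**Reading the set definitions together.**
- A woman first medicated after Visit 3 fails the MITT condition. The PP time-point wording would have kept her Visit 3 result, but PP sits inside the MITT and cannot bring her back.
- LOCF (section 10.8) fills gaps for women in the MITT and PP sets. It does not restore women who were removed.
- The loss of Visit 3 data concerns only women first medicated after Visit 3. A woman with no post-baseline assessment has no Visit 3 outcome to lose.

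**Possible size of the bias.** The protocol gives no exclusion rate, so the shares below are assumptions. If a share q of non-cures is deleted from an arm with true cure rate p, the expected rate becomes p / [p + (1−p)(1−q)]. The error rates come from a simulation of one active arm against placebo: 33 per arm, 400,000 runs, chi-square test at 0.048, equal true cure rates, and deletion in the active arm only.

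| True cure rate, both arms | q | Active arm appears as | False difference | Two-sided error |
|---|---|---|---|---|
| 15% | 15% | 0.15/0.8725 = 17.2% | 2.2 points | 5.6% |
| 30% | 15% | 0.30/0.895 = 33.5% | 3.5 points | 6.1% |
| 50% | 15% | 0.50/0.925 = 54.1% | 4.1 points | 6.3% |
| 15% | 30% | 0.15/0.745 = 20.1% | 5.1 points | 8.2% |
| 30% | 30% | 0.30/0.79 = 38.0% | 8.0 points | 9.7% |
| 50% | 30% | 0.50/0.85 = 58.8% | 8.8 points | 10.6% |

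With no deletion the simulated error is 4.7% to 5.3%. With the same q in both arms it stays near 5% and the mean false difference is zero. Under the plan's 50% against 15%, q = 15% in both arms gives 54.1% − 17.2% = 36.9 points instead of 35.

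**Direction.** Take 33 women with 16 cured (48.5%). Deleting five non-cures gives 16/28 = 57.1%, which is 8.7 points too high. Deleting five cures gives 11/28 = 39.3%, which is 9.2 points too low. The sign depends on who is deleted and from which arm.

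**The case against.** The sponsor has a reason for the rule. Section 6.9 says that antibiotics would confound the endpoints, and an unrelated antibiotic might clear bacterial vaginosis (BV) and be credited to the gel. The routes to exclusion are also narrow:
- rescue antibiotics keep a woman in the MITT, so the main treatment-failure route is retained;
- oral antifungals do not exclude, and sections 7.2.6.4 and 7.3.5 favour oral treatment;
- section 7.1.6 asks every withdrawn woman to attend a Withdrawal Visit with Amsel assessment and Gram stain, and those who attend have a post-baseline assessment;
- section 10.3 has evaluability decided blind.

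All of this stands and limits the likely number of deletions. It does not repair the rule. Blinded application does not help when the event itself can depend on treatment, and confounding by antibiotics can be handled without deletion.

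Some stronger readings are tempting but unsupported:
- A reader might assume that every excluded woman is a non-cure. With 10% excluded per arm the observed difference is then 0.50/0.90 − 0.15/0.90 = 38.9 points. With 15% excluded on active and 5% on placebo it is 0.50/0.85 − 0.15/0.95 = 43.0 points. Nothing in the protocol supports that assumption or that imbalance, and section 10.4 ties the 50% and 15% to evaluable subjects.
- A reader might infer that the bias could never be checked. A Randomized Dataset is defined, and section 6.9 keeps collecting data on these women. What is missing is an efficacy analysis that uses them.
- A reader might call the PP time-point wording void. It is ineffective only for these drugs. It still works for other barred products, such as the spermicides in section 7.3.5, which do not remove a woman from the MITT.

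**Conclusion.** The point holds as a defect in the definition of the primary efficacy set. Following the protocol exactly removes dosed women for events after randomisation, discards outcomes already collected (including valid Visit 3 results), and leaves no assigned efficacy analysis that keeps these women.

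The bias is a risk of uncertain direction. One-sided deletion of 15% of non-cures adds about 2 to 4 points and takes the two-sided error to about 5.6% to 6.3%. Deletion of 30% takes it to about 8% to 11%. The 30% case is heavy: at a 15% cure rate it means losing 0.30 × 0.85 = 25.5% of an arm, more than the planned 15% drop-out. If exclusions are few or balanced, the effect is small. These figures rest on assumed shares and on the deleted women being non-cures. The statistical analysis plan was not available, but the protocol itself fixes this set as the one for all efficacy endpoints.

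**What to change.** 1. Base the primary efficacy analysis on all eligible randomised women who took at least one dose, by assigned arm. Women whose screening Nugent score proves to be below 4 may be left out, because that criterion refers to their state before randomisation.
2. At TOC, count as not cured a woman who took an excluded antibiotic or a vaginal antifungal before TOC, or who has no TOC assessment. This is one strategy among several, but it prevents antibiotic-induced cures being credited to the gel without deleting anyone.
3. Apply the medication rule per time point, so that a Visit 3 outcome obtained before the medication is kept.
4. Keep the present MITT definition as a sensitivity analysis, and align the exclusion sentence in section 6.9.
5. Separately, reconcile sections 7.2.6.4 and 7.3.5 (withdrawal) with sections 6.9 and 8.5 (continued visits) for women needing a vaginal antifungal, because this decides whether later outcome data exist.

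The cost is protocol wording, slightly less favourable cure rates, and some power. If a share d of women is affected and counted as not cured, the rates become 0.50(1−d) and 0.15(1−d). With 33 per arm at alpha 0.048, power is 84.5%, 81.3% and 77.9% for d = 5%, 10% and 15% (assumed shares). Deleting the same shares at random gives 85.5%, 83.5% and 81.2%. At d = 15%, 35 per arm would be needed for 80% power.
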